## Background and significance

### *Lactogenesis*

Stage I lactogenesis (secretory initiation) starts around 16 weeks gestation when high levels of estrogen, progesterone, and prolactin stimulate anatomic growth of breasts (1). High levels of estrogen and progesterone antagonize prolactin's synthesis of lactose. Stage II lactogenesis (secretory activation) starts after the removal of the placenta with a rapid drop in progesterone. The fall in progesterone removes the antagonizing effect on prolactin to start milk production, resulting in swelling of the breasts and milk production that starts 2-3 days postpartum. Breast engorgement occurs when lactation supply exceeds what is expressed from breasts. In the absence of physical stimulation, lactation eventually stops. Among those who do not breastfeed, milk leakage and breast pain begin between 1 to 3 days postpartum and engorgement begins between 1 and 4 days postpartum, all symptoms peaking 4 days postpartum and continuing up to three weeks (6).

### *Lactogenesis in second-trimester abortion or loss*

Breast pain following second-trimester abortion is common. In a prospective, longitudinal study that followed pregnant people after a 14-20 week fetal loss, 50% reported breast tenderness, 45% engorgement, and 20% milk leakage on day 3 post-procedure (2).

### *Emotional distress*

A prior qualitative study of pregnant people with a fetal demise occurring in the late second trimester found that they universally did not expect to lactate (7). Prior qualitative work surrounding mid-trimester perinatal loss suggests that breast engorgement and milk leakage causes physical pain and emotional distress (3).

### *Nonpharmacologic treatment of breast engorgement*

Managing painful engorgement in those choosing not to breastfeed has been described by physicians and midwives for centuries. Midwifery techniques including belladonna ointment, intermittent expulsion, ice packs, and analgesics have been described but not rigorously studied for superiority. A Cochrane Review of

nonpharmacologic interventions for breast engorgement found that there was no evidence that any non-pharmacologic intervention resulted in a quicker resolution of symptoms (8).

## Preliminary work

We conducted a double-blinded, block-randomized superiority trial comparing cabergoline 1 mg once to placebo for preventing bothersome breast engorgement after later second-trimester (18-28 weeks gestation) uterine evacuation (5). At baseline, report of breast symptoms was similar between people randomized to receive cabergoline and those randomized to placebo. On day 4, significantly fewer participants reported any breast symptoms (our primary outcome) in the cabergoline group compared to placebo (27.8% vs 97.0%,  $p<0.001$ ) This difference was significant in all four domains of breast symptoms: engorgement (RR 0.17 [95% CI 0.07-0.45]), breast tenderness (RR 0.18 [95% CI 0.08-0.42]), leaking milk (RR 0.36 [95% CI 0.24-0.53]), and requiring pharmacologic pain relief (RR 0.39 [95% CI 0.26-0.59]). On day 4, 2.8% of those randomized to cabergoline reported significant bother from breast symptoms compared to 29.7% randomized to placebo ( $p=0.001$ ). In an exploratory analysis of those less than 20-weeks gestation (cabergoline n=10, placebo n=9), 30.0% of those receiving cabergoline reported breast symptoms on day 4 compared to 100% of those that received placebo. While underpowered to make definitive claims on efficacy at this earlier gestational age, this provides us reassurance to proceed with the proposed study.

## Project design and methods

### *Study Locations*

Patients will be recruited at Stanford Gynecology Clinic in Palo Alto, CA and Planned Parenthood Mar Monte (PPMM) in San Jose, CA. Stanford University is a large tertiary care center with patients referred from the seven Perinatal Diagnostic Centers (PDCs) across Northern California with fetal anomalies as well as local independent clinics. Medicaid covers abortion care. Stanford University has an established relationship with PPMM, which includes providing regular abortion care services and collaborating on research. Our affiliation with this high volume, outpatient facility allows us to efficiently recruit study subjects, making this a feasible project. Many patients at PPMM receive abortion funds to pay for their abortions. The multi-site design will ensure a large catchment area of geographically and socioeconomically diverse patients to increase external validity.

### *Research Design and General Methodological Approach*

The proposed study is similarly designed as a double-blinded, placebo-controlled, gestational-age stratified (16/0-17/6, 18/0-19/6 weeks gestation) superiority trial to evaluate cabergoline's role in relieving breast engorgement after second-trimester abortion or fetal demise. We will again capture breast symptoms using the validated Bristol Breast Inventory (9). A superiority design was selected as cabergoline is fairly expensive with possible side-effects. For this study to be practice-changing, cabergoline needs to demonstrate clear superiority over placebo.

The use of cabergoline for lactation inhibition after a third trimester delivery has been clearly established (4). Our own work has recently been presented and published, leading to inclusion of cabergoline into more clinical protocols more in the late second trimester (5). The aim of this study is to establish cabergoline's benefit in the early second trimester – a more common experience among pregnant people. As many free-standing, independent clinics only offer abortion care to 19 weeks 6 days gestation, we want to ensure that there is evidence for using cabergoline in our broader community.

We estimate that 15 subjects in each gestational-age strata (16/0-17/6 and 18/0-19/6 weeks gestation) are required to show a 45% decrease in those reporting breast symptoms compared to the control group, with a power of 0.8 and an alpha of 0.05. We plan to recruit 72 subjects, anticipating 10% missing data and loss to follow up.

### Day #0 – Pre-operative visit/Cervical preparation visit

Eligible patients who are scheduled for an abortion or are diagnosed with an intrauterine fetal demise between 16-20 weeks gestation will be approached to enroll in the study. A research staff member will obtain informed consent and randomization will occur. Basic demographic information will be collected and entered into REDCap by a research coordinator (10). Standard demographics, gender identity, prior breastfeeding/ chestfeeding experience, and prior breast surgery will be asked of participants. A baseline Bristol Breast

Inventory questionnaire will be performed to establish existing breast symptoms related to pregnancy followed by a 7-point Likert bother scale. Patients will be randomized and drug distributed (cabergoline or identical placebo) to be taken after the procedure on day #1.

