## Specific aims

Lactogenesis is a two-stage physiologic process of developing the ability to secrete milk that starts in the 16th week of pregnancy and continues after delivery, peaking at day 4 postpartum, regardless of the birth outcome (1). Breast pain following second-trimester abortion is common (2). Breast engorgement and milk leakage following second-trimester perinatal loss and abortion can cause both physical pain and emotional distress (3). Dopamine agonists have previously been shown to be safe and effective in lactation inhibition for third-trimester fetal/neonatal loss or for those with contraindications to breastfeeding (4). Our own research recently found that among those seeking abortion care or management of fetal demise 18-28 weeks gestation, significantly fewer people who received a single dose of cabergoline reported any breast symptoms compared to placebo (5). Fewer than 1% of abortion nationally occur this late in pregnancy; most free-standing clinics provide abortion care for those less than 20 weeks. In our original study, we were underpowered to specifically make claims about those 18-20 weeks, and those 16-18 weeks were excluded. As there is biologic plausibility that lactogenesis starts as early as 16 weeks, this follow-up study seeks to determine if cabergoline is beneficial earlier in the second-trimester.

Therefore, we are hoping to answer whether cabergoline is superior to placebo at preventing symptomatic breast engorgement after early second-trimester abortion or loss. We will conduct a double-blinded, randomized, placebo-controlled, gestational-age stratified superiority trial of those undergoing abortion or intrauterine fetal demise between 16 and 20-weeks gestation at Stanford Health Care and evaluate the following aims:

**Aim 1** (Primary outcome). Determine if fewer pregnant people receiving cabergoline have breast symptoms post abortion/ post fetal expulsion compared to placebo. Participants will complete a survey to assess symptoms, using the validated Bristol Breast Symptoms Inventory at baseline and on days 2, 4, 7, and 14 post procedure. Based on physiology and prior symptom data, Day 4 will serve as our primary outcome.

**Aim 2** (Secondary outcomes). Determine if those receiving cabergoline report higher satisfaction, acceptability, and similar side-effects compared to placebo.

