#### *Data Management & Analysis*

Stanford University has a license for the RedCap data management system (10). REDCap is a web-based application that is secure, reliable, and HIPAA-compliant for storing research study data. REDCap is designed with built-in features to address confidentiality and compliance requirements. Electronic, online surveys will be sent via text message over RedCap on Days 2, 4, 7, 14. Data associated with patient health identifiers (PHI), including the signed informed consent, will be collected electronically. REDCap allows for easy data download into SAS or other statistical software programs. No data will be collected on paper forms. SAS OnDemand will be used for data analysis. Data will be analyzed with parametric or non-parametric statistical tests, as

appropriate. Stratified analysis and logistic regression will be performed to assess demographic characteristics as predictors of breast symptoms and associated distress.

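### The Day 4 comparison gives no stated role to the gestational-age stratum or to baseline symptoms; adjusting for the stratum is a near-free improvement, and adjusting for baseline a conditional one

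*Combined protocol and SAP*

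**What the plan says.** Under Research Design and General Methodological Approach the study is a "gestational-age stratified (16/0-17/6, 18/0-19/6 weeks gestation) superiority trial". The same section gives 15 subjects per stratum for a "45% decrease in those reporting breast symptoms compared to the control group", with power 0.8 and alpha 0.05, and a total of 72 that allows for 10% missing data and loss. It does not say whether 15 is per arm, whether the 45% is absolute or relative, or what placebo rate was assumed.

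Under Day #0, a baseline Bristol "Inventory questionnaire will be performed to establish existing breast symptoms related to pregnancy", together with a bother scale. Study drug is handed out then, "to be taken after the procedure on day #1". That section mentions randomisation both before and after the questionnaire. The drug is blinded and not yet taken, so baseline is a legitimate covariate in either order.

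Under Data Management & Analysis, comparisons use parametric or non-parametric tests as appropriate. The only modelling named is this: "Stratified analysis and logistic regression will be performed to assess demographic characteristics as predictors of breast symptoms and associated distress". That concerns demographic predictors, not the treatment effect. No section says whether the Day 4 comparison is pooled across strata, adjusted for stratum, or made within each stratum.

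**The concern.** When allocation is balanced within strata and the strata have different symptom rates, a standard error (SE) that ignores the strata is too wide. The test is then conservative and gives away power. A baseline that predicts Day 4 symptoms can also reduce the variance of the treatment estimate. Both variables are already collected.

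A difference between strata is possible, though the documents do not show one. The team's placebo rates are 97.0% at 18-28 weeks and 100% of nine participants under 20 weeks ("30.0% of those receiving cabergoline reported breast symptoms on day 4 compared to 100% of those that received placebo"). That trial started at 18 weeks, so those nine all lie in the range of the upper stratum; as Specific aims puts it, "we were underpowered to specifically make claims about those 18-20 weeks, and those 16-18 weeks were excluded". The cited 14-20 week cohort had lower figures: "50% reported breast tenderness, 45% engorgement, and 20% milk leakage on day 3 post-procedure". Its any-symptom rate on day 3 was therefore at least 50%, but need not have been near 97%.

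**Working it through.** **1. The plan's own figure.** Take a placebo rate of 97.0% (Preliminary work; an assumption here) and a 45% relative decrease: p1 = 0.97, p2 = 0.55 x 0.97 = 0.5335, mean 0.75175. The pooled-variance formula for two proportions, two-sided 0.05, power 0.8, is

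n = [1.96 √(2 x 0.75175 x 0.24825) + 0.8416 √(0.97 x 0.03 + 0.5335 x 0.4665)]² / 0.4365² = 14.1, so 15 per arm.

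A 45-point absolute decrease (97% v 52%) gives 13.5, so 14. The stated 15 is thus reproduced as a number per arm within a stratum. If both arms share the 15 (7 or 8 per arm), power at 97% is only about 0.47 to 0.55 by the same approximation.

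**2. Pooled or per stratum.** 72 x 0.9 = 64.8 analysable, taken as 32 per arm, or 16 per arm per stratum (1:1 allocation and equal strata assumed). At 97% v 53.35%, exact Fisher power is 0.80 with 16 per arm (one stratum) and 0.99 with 32 per arm (pooled). The two readings are far apart, and the stated 0.8 sits close to the per-stratum one. All power figures below are for the pooled comparison.

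**3. The stratum term.** Assume null rates of 50% (16/0-17/6) and 97% (18/0-19/6), mean 73.5%, in both arms.

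- SE ignoring strata: √(2 x 0.735 x 0.265 / 32) = 0.110.
- True SD with balanced allocation within strata: average within-stratum variance (0.2500 + 0.0291)/2 = 0.1396, so √(2 x 0.1396 / 32) = 0.093.
- Effective critical value 1.96 x 0.1103/0.0934 = 2.32, so two-sided Type I error is about 0.021.

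Simulation agrees: 0.019 to 0.024 unadjusted, about 0.05 with the stratum term. With the lower stratum at 60% or 70% instead, the unadjusted error is about 0.03 or 0.04. For power under a 45% relative decrease (50/97% strata, baseline odds ratio 4), the unadjusted test gives 0.82 and the stratum-adjusted test 0.85; adding baseline gives 0.88.

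If allocation is not balanced by stratum, the unadjusted test has about the right size (0.05), and the stratum term cuts the null SD from about 0.111 to 0.095. With equal strata the term changes power by at most 0.3 points.

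**4. The baseline term.** Model: Day 4 status from a logistic model with a yes/no baseline (prevalence 50% assumed), calibrated to the placebo rate and to 0.55 times it. Analysis: linear risk-difference model, HC1 robust SE, t reference, equal strata, 20,000 simulated trials per row. Power, unadjusted -> stratum + baseline:

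| Placebo rate | Odds ratio 1 | Odds ratio 4 | Odds ratio 10 |
|---|---|---|---|
| 50% | 0.476 -> 0.461 | 0.479 -> 0.496 | 0.479 -> 0.561 |
| 60% | 0.626 -> 0.594 | 0.622 -> 0.633 | 0.617 -> 0.700 |
| 70% | 0.757 -> 0.731 | 0.755 -> 0.768 | 0.755 -> 0.831 |
| 80% | 0.873 -> 0.862 | 0.869 -> 0.888 | 0.869 -> 0.926 |

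At 90% the changes are -0.3, +0.8 and +1.9 points; at 97-100% they are within 0.2 points. At placebo rates of 60-80% the break-even lies between odds ratios 2 and 4. In that range, with baseline prevalence of 10% or 90%, the change is -2.6 to 0.0 points at odds ratio 4 and -1.1 to +2.1 at odds ratio 10. If the 45% is absolute, unadjusted power at 60-80% is already 0.971 to 0.976.

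**5. Why not ordinary logistic regression.** If the placebo rate is 97%, the chance that all 32 placebo participants have symptoms is 0.97^32 = 0.38 (0.97^16 = 0.61 for the 16 in one stratum). The fitted treatment odds ratio is then infinite. Linear risk-difference and Mantel-Haenszel estimates do not have this problem.

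**The case against.** The strongest reply is that this is a preference. A randomised unadjusted comparison is valid, and the documents give no baseline prevalence, no baseline-to-Day 4 association and no rate for the lower stratum. Preliminary work says only that baseline symptoms were similar between arms. If baseline is not prognostic, adjusting for it loses power. That stands, and it is why baseline ranks second here.

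The reply also says that the too-wide SE depends on allocation balanced within strata, and that no section describes blocks or an allocation method. That stands too. But without such balance the stratum term gains precision instead, so it helps in either case if the strata differ.

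A third point is that per-stratum sizing may mean a per-stratum primary comparison, in which a stratum term does nothing. The arithmetic fits that reading, but the documents do not state it.

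Finally, a binary any-symptom outcome is called primary only for the earlier trial. The sample-size sentence here counts participants reporting symptoms, so a binary outcome is a reasonable reading, though the plan should confirm it.

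A reader might infer that the plan's analysis is biased, or that the trial is underpowered without adjustment. Neither follows. The unadjusted estimate is unbiased, and at the team's own placebo rates the pooled test has power of about 0.99.

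**Conclusion.** The point holds as an optional improvement, with medium confidence. The stratum is in the design and the sizing but not in the stated analysis, and baseline is collected without a stated use.

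- **Stratum:** worth about 3 points of power and a correctly sized test if the strata differ as much as 50% v 97%; at most 0.3 points lost if they do not.
- **Baseline:** about -3 to -1 points if not prognostic, +1 to +2 at odds ratio 4 and +6 to +8 at odds ratio 10. This is for a pooled analysis of about 64 participants, a relative 45% decrease, equal strata, baseline prevalence 50% and placebo rates of 50-80%.

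It would be wrong to read this as an assured gain in precision from both terms. Under balanced allocation the stratum term corrects the SE and leaves the estimate's precision unchanged, and the baseline gain rests wholly on assumed values. None of these figures carries over to a within-stratum comparison.

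**What to change.** Before unblinding, state that the primary Day 4 comparison is pooled across strata and adjusted for gestational-age stratum. Estimate it as a risk difference from a linear model with HC1 robust SE and t reference, or by Mantel-Haenszel. Report the unadjusted and per-stratum differences beside it, and avoid ordinary logistic regression for this comparison. Say whether the power of 0.8 refers to the pooled or the per-stratum comparison.

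Baseline any-symptom status (yes/no) may be added as a second covariate if the team expects it to be clearly prognostic. That choice should also be fixed in advance. At a 70% null rate, reporting whichever of the unadjusted and fully adjusted tests is significant has Type I error of 0.067 (odds ratio 4) or 0.074 (odds ratio 10).

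The cost is SAP wording only, with no new data. The stratum term risks at most 0.3 points of power. At placebo rates of 60-80% and a relative 45%, baseline adjustment risks about 1 to 3 points (up to 3.7 at baseline prevalence of 10% or 90%) if neither variable is prognostic.

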#### Day #1 – Procedure/ Induction Day

Dilation and evacuation (D&E) (procedural abortion) is performed in the outpatient gynecology clinic or ambulatory surgical center, depending on patient preference and other medical considerations. Those seeking induction abortion (medication abortion) will be admitted to Labor & Delivery until fetal expulsion occurs. All participants will receive standard information on support bras, analgesics, and cold compacts. Discharge instructions will instruct patients to take the study drug upon returning home after discharge to increase external validity outside of a trial setting. Patient will later be asked if they took the drug on day #1.

#### Days # 4-14 – Follow-up

Electronic, online surveys regarding breast symptoms using the Bristol Breast Inventory, and a 7-point Likert Scale to assess bother of symptoms and side effects will be collected on Days 2, 4, 7, and 14. Surveys will be sent via text message over RedCap at 08:00. A phone call will be made to participants between 17:00-20:00 if the survey is not completed that day.

An electronic gift card will be sent to the participant after 14 days. Participants will receive [REDACTED] per survey completed with a [REDACTED] bonus for completing all surveys on time for a maximum of [REDACTED] for full participation. With consent, the gift card will be distributed by e-mail or mobile phone number via Tango. Participants will have the opportunity to forego the gift certificate and donate funds to a reproductive health organization.

#### *Criteria for Selection of Subjects*

Inclusion: pregnant people, ages 18 years or older; intrauterine pregnancy between 16/0-19/6 weeks of gestational age (by ultrasound dating performed prior to or same day of enrollment visit); consented for an induced, elective abortion or undergoing management of demise; English or Spanish speaking, able to consent for a research study, literate in English or Spanish; willing to comply with study procedures and follow-up; access to a smart phone throughout the study.

Exclusion: prior mastectomy, currently breastfeeding, currently receiving dopamine agonist therapy for other indication (prolactinoma, Cushings syndrome, acromegaly, restless leg syndrome), contraindication to cabergoline (as per package insert), current use of dopamine antagonists (phenothiazines, butyrophenones, thioxanthenes, or metoclopramide)

#### *Subject Recruitment and Allocation*

Subjects will be recruited from Stanford Gynecology Clinic or Planned Parenthood Mar Monte on the day of their Family Planning consultation, after consent for but prior to abortion, or after diagnosis of intrauterine fetal demise. Only patients in the appropriate gestational ages will be approached. Potential participants will be screened for the study and if eligible and willing to participate in the project, they will be consented for the study.

#### *Description of Drugs and Devices*

Cabergoline is a long-acting dopamine receptor agonist with a high affinity for D2 receptors. It is FDA approved for the treatment of hyperprolactinemic disorders, either idiopathic or due to pituitary adenomas (FDA package insert). We will be using cabergoline off-label.

#### *Data Management & Analysis*

Stanford University has a license for the RedCap data management system (10). REDCap is a web-based application that is secure, reliable, and HIPAA-compliant for storing research study data. REDCap is designed with built-in features to address confidentiality and compliance requirements. Electronic, online surveys will be sent via text message over RedCap on Days 2, 4, 7, 14. Data associated with patient health identifiers (PHI), including the signed informed consent, will be collected electronically. REDCap allows for easy data download into SAS or other statistical software programs. No data will be collected on paper forms. SAS OnDemand will be used for data analysis. Data will be analyzed with parametric or non-parametric statistical tests, as

appropriate. Stratified analysis and logistic regression will be performed to assess demographic characteristics as predictors of breast symptoms and associated distress.

